Patient recruitment and enrollment will take place at urology outpatient clinics at a tertiary university teaching hospital. In 2017, on average 16 biopsy-naïve men with raised serum PSA underwent TRUSB per month. It is therefore estimated that the study will complete within 26 months of commencement. The start date of the study will be 1st April 2019, and the estimated completion date for recruitment will be 1st June 2021.

Statistical analysis

Primary outcome analysis will be based on intention to treat sample as well as per protocol sample.

Primary endpoint is difference in proportion of patients with PCa detected between the two cohorts based on histopathological analysis. Absolute differences in PCa detection rate will be calculated with 95% CIs. If lower bound of 97.5% CI for the difference in cancer detection rates of LA TP biopsy compared with TRUS biopsy is greater than -5%, then TP biopsy will be deemed non-inferior. If lower bound is greater than 0, TP will be deemed superior. Comparisons will be made concerning the basic characteristics between the two arms of participants. If any imbalance were identified, a multivariable logistic regression analysis will be carried out, with clinically significant PCa as the dependent variable and group as the independent variable. Any baseline characteristics imbalance will be used as a covariate.

Effect sizes concerning secondary outcomes will be presented with 95% CIs. For binary outcomes, differences between the two arms will be calculated with 95% CIs. Any imbalance between the two arms will again be accounted for with a multivariable logistic regression analysis. For continuous outcomes, mean differences in outcomes between the two study arms will be calculated with 95% CIs. Imbalances identified between the two groups will be accounted for in a multivariable linear regression analysis. Non-parametric test will be used if any secondary outcomes were found not normally distributed. All statistical analysis will be carried out using the SPSS software.

Primary end-point

Primary outcome is proportion of participants identified with PCa, assessed on a per patient basis from each individual's biopsy histopathological analysis report (i.e. comparison of absolute cancer detection rate). Definition of PCa is presence of any PCa regardless of grade on histopathology. Definition of clinically significant PCa is any core containing Gleason grade 3+4 disease or above. Timeframe for

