assessment will be when histopathology reports are available, usually expected to be within 14 days following biopsy procedures.

Secondary end-points

Secondary outcomes, tools for assessment, and their corresponding timeframe for assessment are summarized in table below.

Secondary outcomes	Assessment tool	Timeframe for
	(if applicable)	assessment
Procedure tolerability	Visual Analogue	Immediately following
	Scale (VAS)	test
Health-related quality of	EQ-5D-5L	Baseline, 24 hours post-
life and patient	questionnaire,	biopsy, and 30 days
satisfaction	IPSS, IIEF	post-biopsy
Proportion of men	Either:	1 week to 30 days post-
developing sepsis	1) admission to	biopsy
	hospital for	
	urosepsis; or	
	2) Presence of	
	rittines in unne at	
Detection rates of	Histopathology	When histonathology
natients with clinically	report	results available
significant PCa (Gleason		expected to be within 14
3+4 or higher)		days following biopsy
Maximum cancer core	Histopathology	When histopathology
length (MCCL, mm)	report	results available,
3 (, , ,		expected to be within 14
		days following biopsy
Proportion of men go on	Clinical records,	After treatment
to undergo definitive	patient interview	decision, expected to be
curative treatment for		within 30 days following
local disease (including		biopsy
surgery and		
radiotherapy)		
Procedure times	Time from start of	During test
(minutes)	ultrasound probe	
	insertion to probe	
Cost por diagnosis of		20 dava post biopay
cost per ulagriosis Of		ou days post-biopsy

Data Access and Handling

To protect patient privacy, all research data will be handled in line with Hospital Authority's or Hospital's policy in handling/storage/destruction of patients' medical records. They would be locked in cabinets where the department/ward keep patients' medical records. Electronic data would be saved in secured computer of the hospital with restricted access. USB Device would not be used for patient information for personal data.

Personal data (name, HKID, address and any other personal identifiable information) will not be recorded on the projects' data sheets or electronic files. A study code will be used.

Any documents or electronic files containing personal identifiable information would be considered as part of the medical record and will be dealt with the same stringent regulations of security according to the hospital policies. The principal investigator/co-investigator will be responsible for the execution of data protection.

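### The adjusted model in the primary-endpoint paragraph takes clinically significant PCa as its outcome, although the primary endpoint is any PCa

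*Protocol*

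**What the plan says.** The Statistical analysis section opens its account of the primary outcome with "Primary endpoint is difference in proportion of patients with PCa detected between the two cohorts based on histopathological analysis". The Primary end-point section settles what counts as an event: "Definition of PCa is presence of any PCa regardless of grade on histopathology". The same section defines the narrower category separately: "Definition of clinically significant PCa is any core containing Gleason grade 3+4 disease or above". The table under Secondary end-points lists detection of that category among the secondary outcomes (the row is broken in the extracted text but legible: "significant PCa (Gleason").

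The primary-endpoint paragraph of Statistical analysis gives the confidence-interval rule, ending with "If lower bound is greater than 0, TP will be deemed superior". It then turns to baseline comparability and provides for a logistic model with several covariates should the arms prove unbalanced. That model is specified as follows: "with clinically significant PCa as the dependent variable and group as the independent variable". The imbalanced characteristics are to enter as covariates.

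The following paragraph deals with secondary outcomes. For binary ones it states: "Any imbalance between the two arms will again be accounted for with a multivariable logistic regression analysis".

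**The concern.** A model placed directly after the primary decision rule should have the primary outcome on its left-hand side. This one has a secondary outcome, a subset of the primary-endpoint cases.

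The protocol foresees imbalance and commits to adjusting for it. Suppose an imbalance appeared in PSA, age or DRE findings, all of which are recorded at baseline. Readers would ask whether the any-PCa difference survives adjustment, and the model as written cannot answer that. Fitting the any-PCa model instead would depart from the protocol's wording, and the change would be made after the imbalance had been seen.

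**Working it through.** **Textual check.** The claim rests on the wording, so the relevant places are set side by side.

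| Place in the protocol | Outcome concerned |
|---|---|
| Statistical analysis, primary-endpoint paragraph: endpoint and decision rule | PCa detected |
| Primary end-point: definition of the event | any PCa, any grade |
| Statistical analysis, primary-endpoint paragraph: regression if imbalance | clinically significant PCa |
| Statistical analysis, secondary-outcome paragraph: regression if imbalance | every binary secondary outcome |
| Secondary end-points table | clinically significant PCa is one of these |

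Three things follow.

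1. The third row does not match the first two, and no other place in the protocol corrects it.
2. The last two rows already give clinically significant PCa an adjusted model, so the third row duplicates it.
3. The word *again* in the secondary-outcome paragraph presents that model as a repeat of what had just been done for the primary outcome. This points to a slip in the third row rather than a deliberate extra analysis, and the protocol gives no reason for switching outcome.

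**Illustration of size.** The protocol states no detection rates, so there is no figure of its own to reproduce.

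- From the protocol: n = 165 per arm (sample-size paragraph).
- Assumed: any-PCa detection p0 = 20%, 30% or 40% on TRUSB; p1 = p0 + 10 points on TPB; half of TRUSB cancers clinically significant (10%, 15%, 20%); none, half or all of the extra 10 points clinically significant.

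Formulas, unadjusted:

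- OR = [p1/(1−p1)] / [p0/(1−p0)]
- SE(log OR) = √[1/(n·p1) + 1/(n(1−p1)) + 1/(n·p0) + 1/(n(1−p0))]

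Worked case, any PCa at 20% against 30%:

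- OR = (0.30/0.70)/(0.20/0.80) = 1.714
- SE = √(1/49.5 + 1/115.5 + 1/33 + 1/132) = 0.258

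All cases, as OR (SE):

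| Outcome modelled | TRUSB any PCa 20% | 30% | 40% |
|---|---|---|---|
| Any PCa | 1.714 (0.258) | 1.556 (0.233) | 1.500 (0.222) |
| Clinically significant, none of the extra cancers significant | 1.00 (0.367) | 1.00 (0.308) | 1.00 (0.275) |
| Clinically significant, half of the extra significant | 1.588 (0.339) | 1.417 (0.292) | 1.333 (0.265) |
| Clinically significant, all of the extra significant | 2.250 (0.324) | 1.889 (0.283) | 1.714 (0.258) |

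Within each column, the standard error for the model as written is between 0.258/0.222 = 1.16 and 0.367/0.258 = 1.42 times that of the any-PCa model.

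The model as written could therefore show no effect where the primary effect is real, or a larger one than the primary endpoint has. It would also do so less precisely.

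**The case against.** The strongest reply concedes the mismatch and disputes its weight.

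- **The model is conditional and decides nothing.** It runs only if imbalance is found, and it carries no success criterion. Allocation is randomised, so the unadjusted comparison is valid without it. This stands, and it limits the consequence to the adjusted analysis.
- **An SAP may repair it.** One may exist and was not available for this review, so the absence of an adjusted any-PCa analysis can be asserted only of the protocol. That limit stands. It does not remove the error, because the protocol does not leave the dependent variable open: it names one, and names the wrong one. An SAP that follows the protocol inherits the mismatch, and one that uses any PCa contradicts the protocol.
- **The odds ratios are assumed and unadjusted.** A multivariable logistic model estimates conditional odds ratios, which generally differ from these. Both points are fair. The table shows only that the two outcomes can give materially different answers; it does not predict this trial's result.
- **The correction is incomplete.** A logistic model on any PCa still yields an odds ratio, which cannot be set directly against an absolute difference or the −5%/0 thresholds. The trigger and the covariates would still depend on observed imbalance. This is true, but these are separate features of the same sentences and do not justify keeping the wrong outcome.

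**Conclusion.** The point holds and should be fixed. The imbalance-triggered regression in the primary-endpoint paragraph is wrong as written: its dependent variable is a secondary outcome, and nowhere does the protocol specify an adjusted model for any PCa.

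The effect is confined to that adjusted analysis. The unadjusted difference in detection rates, the intention-to-treat and per-protocol samples, the −5%/0 rule, the sample size and the error rate are all untouched. The protocol does not say what role the adjusted model has beside the confidence-interval rule, so describing it as a check on the primary result is an interpretation drawn from its placement.

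Under the stated assumptions, the model as written would address an odds ratio between 1.00 and 2.25 where the any-PCa value is 1.50 to 1.71. The textual finding does not depend on those assumptions.

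**What to change.** In the regression sentence of the primary-endpoint paragraph, replace clinically significant PCa with any PCa (the primary endpoint) as the dependent variable. Leave clinically significant PCa to the logistic regression already provided for binary secondary outcomes in the next paragraph. If an SAP exists, confirm that it names the same outcome.

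The cost is one term in one sentence, with no additional model, data or patients and no change to sample size or power.

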All patients referred with a raised serum PSA or abnormal DRE will be seen in the urology specialist unit outpatient clinic (OPD), where patients will be screened and assessed for eligibility for the study. All patients must satisfy all inclusion criteria and none of the exclusion criteria outlined in the table below.

Inclusion criteria	Exclusion criteria
1. Patients between ages 40 –	1. Patients who are unable to
80	provide written informed
	consent
2. Serum PSA ≤20ng/mL	Known history of prostate
	cancer
Suspected tumour clinical	Contraindication to prostate
stage ≤T2 on DRE	biopsy
No previous history	Had pre-biopsy mpMRI
prostate biopsy	
5. Medically fit to undergo	5. Rectal abnormality precluding
procedures according to	transrectal ultrasound
study protocol	

If eligible, informed consent will be obtained. Baseline characteristics will be recorded, such as age, height, weight, allergies, past medical history, family history of PCa, drug history, presenting PSA and DRE findings. Baseline urine and blood samples will be taken. Baseline IPSS, EQ-5D-5L and IIEF questionnaires will be filled by each participant. Eligible patients will be randomized to either the LA TRUSB arm or the LA TPB arm. Randomisation will be executed per participant with a third-party statistical software using a computer-generated randomization tool, following completion of informed consent procedure. Equal allocation between both arms will be performed, using random permuted blocks of varying size. In order to ensure allocation concealment, block sizes will not be disclosed and randomisation codes will be obtained through a web-based application.

Procedures will be carried out within 30-60 days following first visit. Procedure in each arm will be carried out according to protocols described below within 60 days of randomisation. All patients on anticoagulants will be advised to stop 7 days prior to biopsy.

For the superiority hypothesis, based on assumptions from results from previous preliminary studies, a sample size of 330 subjects (165 per group) will achieve 80% power to detect superiority of LA TPB over TRUSB. The calculation used a one-sided Z test assuming superiority margin of 10% and the significance level at 0.05. Estimating up to 10% of patients will withdraw from the study or loss to follow-up, 364 patients will need to be recruited for the study (182 patients per arm).

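### Quality-of-life scores are compared without their baseline unless an imbalance is noticed, which gives up precision and lets the data choose the model

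*Protocol*

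**What the plan says.** Under Study design and method, the protocol states: "Baseline IPSS, EQ-5D-5L and IIEF questionnaires will be filled by each participant". The text places this before randomisation. The table under Secondary end-points lists the same three instruments for health-related quality of life and patient satisfaction, with assessments beginning "Baseline, 24 hours post"-biopsy and ending at 30 days.

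The Statistical analysis section then fixes three rules for continuous secondary outcomes:

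- The default: "For continuous outcomes, mean differences in outcomes between the two study arms will be calculated with 95% CIs".
- The exception: "Imbalances identified between the two groups will be accounted for in a multivariable linear regression analysis".
- The fallback: "Non-parametric test will be used if any secondary outcomes were found not normally distributed".

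No sentence names a scale's own baseline score as a covariate for its follow-up score, and none says what counts as an imbalance. The protocol also leaves open whether the outcome compared is the post-biopsy score or the change from baseline.

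**The concern.** In a randomised trial, the reason to adjust for a baseline score is that it predicts the follow-up score, not that the arms happen to differ on it. The protocol makes adjustment depend on an observed difference. This has two consequences.

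- **Precision.** When no imbalance is noted, the baseline score is left out of the model even though each man has supplied it. The interval for the difference between biopsy routes is then wider than it need be.
- **A data-dependent model.** Without a criterion, whether the adjusted or the unadjusted difference is reported can be settled after the data are seen. The normality rule adds a second switch, to an unnamed test with no stated baseline term.

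The estimates affected are the differences in urinary symptoms, erectile function and general health after biopsy.

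**Working it through.** **The plan's own figure.** There is none for this point: the protocol gives no standard deviation, target difference, correlation or power for EQ-5D-5L, IPSS or IIEF. The 165 evaluable men per group come from the primary-endpoint calculation ("a sample size of 330 subjects (165 per group) will achieve 80% power to detect superiority of LA TPB over TRUSB"). That figure cannot be reproduced because the assumed detection rates are not stated. It is used here only as the number per arm.

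**Inputs.** n = 165 per arm (protocol). Two-sided 0.05, to match the 95% intervals (protocol). The correlation r between baseline and follow-up is an assumption, shown from 0.3 to 0.8. Equal variance σ² at baseline and follow-up is also assumed.

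**Formulas.** Variance of the outcome entering the between-arm comparison, in units of σ²:

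- raw follow-up score: 1
- change from baseline: 2(1 − r)
- ANCOVA: 1 − r²

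The interval-width ratio is √(1 − r²) for ANCOVA against raw scores. Against change scores it is √[(1 − r²) / (2(1 − r))] = √[(1 + r)/2].

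| r | ANCOVA variance | Change-score variance | Narrower than raw | Narrower than change |
|---|---|---|---|---|
| 0.3 | 0.91 | 1.40 | 5% (ratio 0.954) | 19% (0.806) |
| 0.5 | 0.75 | 1.00 | 13% (0.866) | 13% (0.866) |
| 0.7 | 0.51 | 0.60 | 29% (0.714) | 8% (0.922) |
| 0.8 | 0.36 | 0.40 | 40% (0.600) | 5% (0.949) |

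**In terms of detectable difference.** For raw scores, 80% power is reached at (1.960 + 0.842) × √(2/165) = 0.308 SD. Multiplying by √(1 − r²) gives 0.294 SD (r = 0.3), 0.267 (0.5), 0.220 (0.7) and 0.185 (0.8). The equivalent number per arm, 165/(1 − r²), is 181, 220, 324 and 458.

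**The imbalance trigger.** The protocol gives no criterion, so suppose, as an assumption, that imbalance means p < 0.05 on the baseline score. Under randomisation about 95% of comparisons per scale would then stay unadjusted. Take a baseline difference of k standard errors that goes unflagged, with no true effect and raw scores compared. The follow-up z-statistic is then normal with mean rk and variance 1 − r². For k = 1.9, the main tail is:

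- r = 0.5: P(Z > (1.96 − 0.95)/0.866), so the conditional type I error is about 12%
- r = 0.7: P(Z > (1.96 − 1.33)/0.714), so it is about 19%

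The opposite tail is negligible. For k = 1 the figures are 4.8% and 3.9%, so the problem is confined to differences that nearly meet the trigger. Averaged over randomisations, the plain unadjusted test keeps its 5%.

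**The case against.** The strongest reply is that nothing here is an error. Randomisation makes the unadjusted difference unbiased and its interval valid. These scales carry no power target and no decision rule. Quality of life is not among the objectives under Aim of study, which are detection, sepsis and tolerability; tolerability is measured by a VAS straight after the procedure and has no baseline. All of this stands, and it limits the point to efficiency and to fixing the model in advance.

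A reader might infer that the plan compares raw post-biopsy means and discards the baseline. The text does not support that. It speaks only of outcomes, and baseline is one of the listed assessment times, so change scores remain possible. Baseline scores can also enter through the regression for identified imbalances.

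A reader might also infer that baseline is a strong predictor, so that differences between men swamp any biopsy effect. The protocol gives no correlation. It schedules procedures 30 to 60 days after the first visit. If the questionnaires are completed at that visit, the 30-day score follows 60 to 90 days later, which could lower r. Even unadjusted, 165 per arm would detect about 0.31 SD with 80% power.

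Finally, covariates for secondary questionnaires usually belong in a statistical analysis plan, and none was available here. That would answer a complaint about missing detail. It does not answer this one, because the protocol states a rule, adjustment only when imbalance is identified, and a plan that always adjusts would depart from it.

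**Conclusion.** The point holds as a minor one. The protocol fixes an analysis rule for EQ-5D-5L, IPSS and IIEF that is valid but inferior to one available at no cost. Which column of the gain applies depends on whether raw or change scores are meant, and its size depends on an assumed r. Over r = 0.5 to 0.8 the interval narrows by 13% to 40% against raw scores and by 13% down to 5% against change scores. At r = 0.3 the gain over raw scores is only about 5%. Fixing the model in advance is worthwhile whatever r is, because it removes a choice that now has no stated criterion.

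The documents do not support a claim of bias, of an invalid interval, or of any effect on the primary endpoint. Nor do they show that a wider interval would be misread as no difference.

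**What to change.** In the Statistical analysis section, add wording to this effect for EQ-5D-5L, IPSS and IIEF:

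- The between-arm difference at 24 hours and at 30 days is estimated by ANCOVA, or by one repeated-measures model covering both times, with the same instrument's baseline score as a covariate whether or not an imbalance is seen.
- The outcome in that model is the score at the stated time, so the choice between raw and change scores is closed.
- Non-normality on these scales is handled within the model, for example by robust or bootstrap intervals, or by a baseline-adjusted rank analysis as a sensitivity analysis. It does not trigger a switch to an unadjusted non-parametric test. Without this sentence the new rule would conflict with the existing fallback.

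The cost is wording only. The baseline scores are already collected, and no visit, patient or questionnaire is added. The change should be made before outcome data are compared by arm.

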biopsy needles directly inserted through the perineal skin rather than bowel, the risk of sepsis is reduced. However, this technique requires multiple needles traversing through the perineum, and requires to be carried out under general anaesthesia (GA). Another disadvantage is a stabilising stepping unit is required to provide a consistent alignment of the ultrasound probe against the prostate in order to carry out the biopsies. Such stabilising stepping units are costly.

A novel but simple transperineal access system device known as PrecisionPoint (Perineologic, Cumberland, MD, USA) has been developed to tackle the aforementioned limitations of TPB. This revolutionary device utilises a single access needle cannula mounted directly on to the ultrasound probe, which acts as an access point traversing through the perineal skin. This design minimises the number of needle punctures through the skin, enabling TPB to be carried out under LA. A stabilising stepping unit is not required with this technique. The device has gained the United States Food and Drug Administration (FDA) approval [11], and results from small contemporary series have already been published with very promising results in terms of cancer detection rate and safety [12].

TRUSB has a poor cancer detection rate and is associated with potentially fatal septic risk. TPB, if able to be carried out under LA as an office-based procedure, can potentially provide a better cancer detection rate with significantly reduced sepsis risk. It has fundamentally a very high potential to become the new gold standard in obtaining prostate tissue for histological diagnosis of PCa.

With an increasing number of men in Hong Kong with elevated serum PSA suspicion of PCa needing prostate biopsy, we strongly feel that it is fundamental to carry out a study to determine the most effective, safe and tolerable prostate biopsy technique which fits with the clinical practice in Hong Kong.

Aim of study

To evaluate whether TPB using a noval transperineal access system under LA is superior to standard 12-cores TRUSB in detecting prostate cancer (PCa), in patients with clinical suspicion of PCa with no prior prostate biopsy.

Other objectives of the study include:

- > To assess whether LA TPB has reduced post-biopsy sepsis rate
- To assess whether patient tolerability with LA TPB is non-inferior to standard TRUSB

Study design and method

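### Patient satisfaction is listed as a secondary outcome, but none of the tools named for it measures satisfaction with the biopsy procedure

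*Protocol*

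**What the plan says.** The relevant row of the Secondary end-points table in the protocol has a label broken over several lines: "Health-related quality of", then "life and patient", then the word satisfaction. Two outcomes therefore share one row. The tool cell lists EQ-5D-5L, IPSS and IIEF and nothing else. The timeframe cell starts "Baseline, 24 hours post" and goes on to 30 days after biopsy.

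The Study design and method section names the same three instruments at entry: "Baseline IPSS, EQ-5D-5L and IIEF questionnaires will be filled by each participant". In that section's order of events this comes before randomisation, and the inclusion criteria admit only men with no earlier prostate biopsy.

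Two other sources of patient report appear in the table, each tied to a different outcome. The visual analogue scale belongs to "Procedure tolerability" and is taken straight after the test. The entry "patient interview" is a source only for the outcome on definitive treatment.

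Among the objectives, the one on patient experience is "To assess whether patient tolerability with LA TPB is non-inferior to standard TRUSB". Satisfaction is not among them.

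**The concern.** A listed outcome needs a measure that can answer it. Here satisfaction takes its tools and time points from quality of life. Those tools are general health and function questionnaires, and they are also scheduled at a point when no biopsy has been done.

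If the plan is followed as written, the report may be silent on a pre-specified outcome, or it may present a health or symptom score under the heading of satisfaction. The second could be misread as men being more content with one biopsy route than the other. An analysis plan cannot repair this later, because it can define how answers are analysed but cannot supply answers that were never collected.

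**Working it through.** The protocol gives no figure to reproduce here. The check is whether the outcome and its tools match.

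1. **Tools in the row.** EQ-5D-5L, IPSS and IIEF. The cell reads as complete, unlike the rows on sepsis, procedure time and cost, which are broken in the text at hand. Study design and method independently names the same three, so a lost fourth tool is unlikely.

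2. **Can these tools record satisfaction with the biopsy?** Every participant completes them at baseline, before allocation, and no participant has had a prostate biopsy before. A questionnaire that can be completed then does not ask how satisfied a man was with the procedure. This step needs only the protocol. The general purpose of the three tools (general health, urinary symptoms, sexual function) agrees with it, but the protocol does not reproduce the questionnaires, so that part is background and not evidence.

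3. **Does the baseline time point fit?** It fits quality of life and function. It cannot fit satisfaction with a procedure that has not yet taken place.

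4. **Is satisfaction measured elsewhere in the protocol?** The visual analogue scale is assigned to tolerability, in its own row and at a different time. Patient interview is assigned to the treatment outcome. No other satisfaction question or rating appears in the text.

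5. **Would one added question be informative?** This describes the proposed remedy, not the size of the flaw. For a yes/no item with n = 165 per arm (the protocol's number before allowing for dropout) and the same proportion p in both arms, the half-width of the 95% confidence interval for the difference is 1.96 × √(2p(1 − p)/n). The values of p are assumptions.
   - p = 0.5: 1.96 × √(0.50/165) = 0.108, about ±11 percentage points
   - p = 0.8: 1.96 × √(0.32/165) = 0.086, about ±9 percentage points
   - p = 0.9: 1.96 × √(0.18/165) = 0.065, about ±6 percentage points

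That is adequate precision for a descriptive secondary outcome, with no change to the sample size.

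**The case against.** The strongest reply is that the protocol says patient satisfaction without saying satisfaction with what. The row pairs it with quality of life, gives it function questionnaires and includes baseline. Read that way, it could mean satisfaction with urinary or sexual function before and after biopsy, and the baseline time point would then make sense. This reading cannot be excluded, and it limits the point: the gap concerns satisfaction with the procedure. It does not rescue the row, because a reader of a trial comparing two biopsy techniques will take an unqualified satisfaction outcome to refer to the technique.

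A reader might infer that the trial will hold no satisfaction data at all, from none of the 364 men to be recruited. The documents do not support that. Items on satisfaction with function may be collected through the named questionnaires, a case report form that is not shown could carry a further question, and the procedure descriptions that the protocol refers to are not in the text at hand. What can be said is that no tool named in the protocol measures satisfaction with the biopsy.

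A reader might also infer that a main argument of the trial is left without data, because the background says it should "determine the most effective, safe and tolerable prostate biopsy technique which fits with the clinical practice in Hong Kong". That sentence speaks of tolerability, which has its own objective and its own scale. Satisfaction is not a stated aim, so the inference fails. Nor does the protocol say that a function score will be reported as preference for a route; that is a risk of the label, not a plan.

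**Conclusion.** The point holds in limited form and is of low severity. Patient satisfaction is a listed secondary outcome, and no named tool measures satisfaction with the biopsy procedure; at most, satisfaction with urinary or sexual function is captured. One secondary outcome is affected. The primary endpoint, the sample size and the stated objectives are untouched.

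The conclusion assumes that the tool cell is complete as it appears and that satisfaction is meant to refer to the procedure. If the investigators meant satisfaction with function, the defect is one of labelling only and the row should say so. The case for changing the plan is that the remedy costs almost nothing, while answers not collected at the 24-hour and 30-day assessments cannot be reliably recovered afterwards.

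**What to change.** Give patient satisfaction its own row in the Secondary end-points table, with one direct question, for example whether the man would be willing to have the same procedure again. Ask it at the 24-hour and 30-day assessments already planned, with no baseline time point. Analyse it as a difference in proportions with a 95% confidence interval, which is already the rule for binary secondary outcomes in the Statistical analysis section. Keep EQ-5D-5L, IPSS and IIEF for quality of life and function.

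The cost is one extra question per assessment and a small edit to the table. If the question is not added, remove patient satisfaction from the existing row so that no health or symptom score is reported under that name.
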